Appendix 1:

Subjective Symptoms VISUAL ANALOG SCALE (VAS)

Not bothersome	Most Bothersome
0 1 2 3 4 5 6 7 8	9 10

SYMPTOMS

Vulvar itching
 Vulvar burning
 Vulvar irritation
 Pain with intercourse
 Tearing of vulvar skin
 Painful urination
 Painful defecation

Objective Signs VISUAL ANALOG SCALE (VAS)

Absent		Mild		Moderate		Severe				
0	1	2	3	4	5	6	7	8	9	10

SIGNS

- White plaques/hypopigmentation
- Cigarette paper, thin skin
- Introital narrowing
- Perianal involvement (figure of 8 shape)
- Loss of labia minora
- Fusion of labia minora
- Phimosis of clitoral hood
- Vulvar fissure
- Erosion

Appendix 2: SKINDEX

These questions concern your feelings over the past 4 weeks about **the skin condition that has bothered you the most**. Check the answer that comes closest to the way you have been feeling.

HOW OFTEN DURING THE PAST FOUR WEEKS DO THESE STATEMENTS DESCRIBE YOU?	NEVER	RARELY	SOMETIMES	OFTEN	ALL THE TIME
1. My skin hurts	 1	 2	 3	 4	 5
2. My skin condition affects how well I sleep	 1	 2	 3	 4	 5
3. I worry that my skin condition may be serious	 1	 2	 3	 4	 5
4. My skin condition makes it hard to work or do hobbies	 1	 2	 3	 4	 5
5. My skin condition affects my social life	 1	 2	 3	 4	 5
6. My skin condition makes me feel depressed	 1	 2	 3	 4	 5
7. My skin condition burns or stings	 1	 2	 3	 4	 5
8. I tend to stay at home because of my skin condition	 1	 2	 3	 4	 5
9. I worry about getting scars from my skin condition	 1	 2	 3	 4	 5
10. My skin itches	 1	 2	 3	 4	 5
11. My skin condition affects how close I can be with those I love.	 1	 2	 3	 4	 5
12. I am ashamed of my skin condition	 1	 2	 3	 4	 5
13. I worry that my skin condition may get worse	 1	 2	 3	 4	 5
14. I tend to do things by myself because of my skin condition	 1	 2	 3	 4	 5
15. I am angry about my skin condition	 1	 2	 3	 4	 5
16. Water bothers my skin condition (bathing, washing hands)	 1	 2	 3	 4	 5

- | | | | | | |
|--|---------------------------------------|---------------------------------------|---------------------------------------|---------------------------------------|---------------------------------------|
| 17. My skin condition makes showing affection difficult |  ₁ |  ₂ |  ₃ |  ₄ |  ₅ |
| 18. I worry about side-effects from skin medications / treatments. |  ₁ |  ₂ |  ₃ |  ₄ |  ₅ |
| 19. My skin is irritated |  ₁ |  ₂ |  ₃ |  ₄ |  ₅ |
| 20. My skin condition affects my interactions with others . . . |  ₁ |  ₂ |  ₃ |  ₄ |  ₅ |

Please turn to next page

These questions concern your feelings over the past 4 week about **the skin condition that has bothered you the most**. Check the answer that comes closest to the way you have been feeling.

HOW OFTEN DURING THE PAST 4 WEEK
DO THESE STATEMENTS DESCRIBE YOU?

NEVER	RARELY	SOMETIMES	OFTEN	ALL THE TIME
-------	--------	-----------	-------	-----------------

- | | | | | | |
|--|---------------------------------------|---------------------------------------|---------------------------------------|---------------------------------------|---------------------------------------|
| 21. I am embarrassed by my skin condition |  ₁ |  ₂ |  ₃ |  ₄ |  ₅ |
| 22. My skin condition is a problem for the people I love . . |  ₁ |  ₂ |  ₃ |  ₄ |  ₅ |
| 23. I am frustrated by my skin condition |  ₁ |  ₂ |  ₃ |  ₄ |  ₅ |
| 24. My skin is sensitive |  ₁ |  ₂ |  ₃ |  ₄ |  ₅ |
| 25. My skin condition affects my desire to be with people |  ₁ |  ₂ |  ₃ |  ₄ |  ₅ |
| 26. I am humiliated by my skin condition |  ₁ |  ₂ |  ₃ |  ₄ |  ₅ |
| 27. My skin condition bleeds |  ₁ |  ₂ |  ₃ |  ₄ |  ₅ |
| 28. I am annoyed by my skin condition |  ₁ |  ₂ |  ₃ |  ₄ |  ₅ |
| 29. My skin condition interferes with my sex life |  ₁ |  ₂ |  ₃ |  ₄ |  ₅ |
| 30. My skin condition makes me tired |  ₁ |  ₂ |  ₃ |  ₄ |  ₅ |

Appendix 3: Vaginal Health Index

	Overall elasticity*	Fluid secretion type & consistency	pH	Epithelial mucosa	Moisture
1	None	None	6.1	Petechiae noted before contact	None, mucosa inflamed
2	Poor	Scant, thin yellow	5.6 – 6.0	Bleeds with light contact	None, mucosa not inflamed
3	Fair	Superficial, thin white	5.1 – 5.5	Bleeds with scraping	Minimal
4	Good	Moderate, thin white	4.7 – 5.0	Not friable, thin mucosa	Moderate
5	Excellent	Normal (white flocculent)	≤ 4.6	Not friable, normal mucosa	Normal

*Lower score corresponds to greater urogenital atrophy

Appendix 4

Patient Global Impression of Improvement

Circle how you feel your symptoms are after treatment:

Much Worse	Worse	Same	Better	Much Better
1	2	3	4	5

Level of satisfaction after treatment

How would you define the level of satisfaction with the treatment?

Very Dissatisfied	Dissatisfied	Same	Satisfied	Very Satisfied
1	2	3	4	5

Appendix 5

The Vulvovaginal Symptom Questionnaire

The following questions were developed to assess skin symptoms of women. The skin surrounding the vagina is called the vulva. Just like skin in other parts of the body, the vulva can sometimes become irritated. Many women experience discomfort in the region of the vulva. These symptoms may be mild, but can sometimes be severe. The following questions will ask you about your vulvar skin symptoms during the past week.

During the past week, have you been bothered by:		
1.	Your vulva itching?	0  No 1  Yes
2.	Your vulva burning or stinging?	0  No 1  Yes
3.	Your vulva hurting?	0  No 1  Yes
4.	Your vulva being irritated?	0  No 1  Yes
5.	Your vulva being dry?	0  No 1  Yes
6.	Discharge from your vulva or vagina?	0  No 1  Yes
7.	Odor from your vulva or vagina?	0  No 1  Yes
8.	Worry about your vulvar symptoms? (for example, that it will spread, get worse, scar, etc.)	0  No 1  Yes
9.	The appearance of your vulva?	0  No 1  Yes
10.	Frustration about your vulvar symptoms?	0  No 1  Yes
11.	Embarrassment about your vulvar symptoms?	0  No 1  Yes
12.	The effects of your vulvar symptoms on your interactions with others?	0  No 1  Yes
13.	The effects of your vulvar symptoms on your desire to be with people?	0  No 1  Yes
14.	Your vulvar symptoms making it hard to show affection?	0  No 1  Yes
15.	The effects of your vulvar symptoms on your daily activities?	0  No 1  Yes
16.	Your vulvar symptoms affecting your desire to be intimate?	0  No 1  Yes
17.	Are you currently sexually active with a partner?	
	 No → Thank you. You are done with this questionnaire.	
	 Yes → Please proceed with the next 4 questions	
18.	The effects of your vulvar symptoms on your sexual relationships?	0  No 1  Yes
19.	Your vulvar symptoms causing pain during sexual activity?	0  No 1  Yes
20.	Your vulvar symptoms causing dryness during sexual activity?	0  No 1  Yes
21.	Your vulvar symptoms causing bleeding during sexual activity?	0  No 1  Yes

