3.0 STUDY DESIGN

Women presenting to the urogynecology clinic will be screened for lichen sclerosus. Vulvar biopsy will be performed for confirmation, and, if eligible, the patient will be consented to undergo baseline questionnaires, photodocumentation of vulvar lesions and randomization. Patient will be randomized to monthly LASER treatment for 3 months or topical STEROID therapy (temovate propionate .05% ointment nightly for one month, three times weekly for 2 additional months, then as needed) in a 1:1 ratio using a computer generated randomization schedule. Grouping assignments will be kept in sealed consecutively numbered, opaque envelopes. Because of the nature of the treatment, it will not be possible to blind patients but the assessor will be blinded to the intervention.

Patient questionnaires include multiple validated scales and surveys to provided reproducible measures of vulvar symptoms as primary and secondary outcomes. Questionnaires will be completed at the intake visit, repeated at 12 weeks after treatment is completed or 6 months from intake, and one year follow up. Subjective symptoms including vulvar itching, vulvar burning, vulvar irritation, pain with intercourse, tearing of the vulvar skin, painful urination, and painful defecation will be rated with a validated visual analog scale (VAS), scaled 0-10, see appendix 1. Higher values correspond to more bothersome symptoms. The Skindex-29 questionnaire is a subjective measure of skin symptoms validated against the Medical Outcomes Study 36-item Short-Form Survey (SF-36)¹⁷, appendix 2. The Skindex-29 was developed in dermatology and modified for use in vulvadynia¹⁸. The Skindex-29 is scored as a sum expressed on a 100-point scale with higher scores indicating lower quality of life. Validated quartiles are used to characterize disease symptoms, emotions, functioning, and overall score as either very little, mild, moderate, or severe¹⁹. Secondary outcomes of patient satisfaction and global impression of improvement will be collected using simple validated visual analog scale from 0-5, much worse to much better, appendix 4. A final subjective measure, the Vulvovaginal Symptoms Questionnaire (VSQ), a validated measure of vulvar symptoms, emotions, life impact, and sexual impact in postmenopausal women will be collected a secondary outcome²⁰, appendix 5. A higher total score on the VSQ corresponds to lower quality of life.

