5.0 SAMPLE SIZE CALCULATION

The study will consist of 2 study groups (LASER vs STEROID therapy). We expect improved subjective and objective results in the LASER group at 3 months post treatment or 6 months from enrollment compared with the STEROID group.

This study is designed as a two-group randomized clinical trial. Sample size calculations were conducted using the absolute change in the Skindex 29 as the primary end point. Our study will reach 80% power to detect a mean difference of 16 points on the Skindex 29 (sd=22 for both groups)²² between the study groups with 24 patients in each group, or 48 in total based on a one-sided two-sample t-test with alpha=0.05. By accounting for 10% attrition, we propose to recruit 52 patients to the study to be randomized with a 1:1 ratio to each group, with a blocked component for those who used topical clobetasol in the past. The Skindex-29 has validated cutoff categories for mildly, moderately, and severely impaired health related quality of life scores, the mean difference between each quality of life measure overall score is between 6 and 7. Therefore, powering the study for a detection of mean difference of 16 points should measure significant quality of life improvement.^{23,24}

Study Timeline:

	Intake Visit	Day 0	2 weeks	4 weeks-14 weeks	6 months	1 year
Vulvar biopsy (if never completed)	X					
Vaginal STEROID or LASER			STEROID daily x 4 weeks LASER monthly x 3 months	STEROID three times weekly x 8 more weeks, then as needed LASER STOP at 12 weeks		
Vaginal Health Index scale (VHIS)		X			X	x
SkIndex-29 Vulvar QoL Questionnaire Vulvovaginal Symptoms Questionnaire (VSQ)		X			X	x
Telephone call to check compliance and answer questions			X	X (8 weeks)		
Photodocumentation		X			X	x
Questionnaire of patient global impression of improvement and satisfaction PGI-I					X	x

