8.0 PROTECTION AGAINST RISK

The proposed study involves changes in provision of program services to study participants. Description of random and blinded nature of the protocols will be explained by the physician in charge of the participant. To avoid or minimize potential risks, frequent monitoring for adverse events will be performed by study staff and the PI.

Risks of clobetasol proprionate include skin irritation, burning, rash and change in skin pigmentation.

Potential adverse reactions to laser use include ocular laser exposure which will be minimized with the use of protective eyewear with an optical density of 4x the treatment wavelength. Pain or mild to moderate discomfort, erythema, swelling, blistering, itching, numbness, change in pigmentation, scarring, and burns are other adverse events including as well as painful intercourse, change (postive or negative) in sexual response, including arousal around clitoris and orgasm. These risks will be minimized with laser use per manufacture instructions with trained personel and avoidance of laser treatment within 5mm of clitoral glans and hood. All known risks will be disclosed to the participants via the informed consent process. All study participants will be closely monitored post treatment for adverse events.

All known risks will be disclosed to the participants via the informed consent process. All study participants will be closely monitored post treatment for adverse events. All study investigators will receive extensive training on the study protocol. Attending staff/surgeons will also receive training on how to operate the laser and the appropriate settings for the vulvar treatment, supervised by the study mentor. Serious adverse events are defined as any untoward medical occurrence that (1) results in death, (2) is life-threatening, (3) requires inpatient hospitalization (4) results in persistent or significant disability or incapacity, (5) is a congenital anomaly/birth defect, or (6) is another medically important condition.

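### Does the lack of a scoring rule for VSQ items 18–21, which women who are not sexually active skip, undermine the between-arm comparison?

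*Combined protocol and SAP*

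**What the plan says.** Section 1.0 lists the VSQ among the secondary outcomes. Section 3.0 describes it as "a validated measure of vulvar symptoms, emotions, life impact, and sexual impact in postmenopausal women", cites a validation reference, and gives its direction: "A higher total score on the VSQ corresponds to lower quality of life". The study timeline in Section 5.0 places it at Day 0, 6 months and 1 year.

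Appendix 5 reproduces the form. Items 1–16 are scored 0 or 1 for every woman. Item 17, which carries no score, asks "Are you currently sexually active with a partner". A woman who answers no reads "Thank you. You are done with this questionnaire". One who answers yes reads "Please proceed with the next 4 questions" and completes items 18–21, also scored 0 or 1.

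Section 12.0 names summaries and tests for questionnaire scores. It gives no VSQ formula and no rule for skipped items. Section 4.0 does not make sexual activity an entry criterion, so both routes through item 17 are open.

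**The concern.** A total built from 16 answers in some women and 20 in others is not obviously one scale. If it is a raw sum, its ceiling is 16 or 20 according to activity at that visit. At 6 months and 1 year that activity is a post-randomisation status.

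The plan also gives a reason why activity might differ by arm. Section 8.0 lists "painful intercourse, change (postive or negative) in sexual response" among the laser risks, whereas the clobetasol risks "include skin irritation, burning, rash and change in skin pigmentation".

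Under a raw sum the score could move against the sexual outcome. A woman who resumes sex after improving could gain up to 4 points, and one who stops because of pain could lose up to 4. The VSQ comparison could then shift for reasons unrelated to items 1–16.

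A related worry concerns the Appendix 1 symptom scale. Its item on pain with intercourse has no not-applicable response, so a 0 may mean intercourse without bother or no intercourse at all. Dyspareunia is part of the primary outcome in Section 1.0.

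**Working it through.** The plan states no VSQ figure, so there is nothing to reproduce first. The inputs from the documents are 16 scored items for all women, 4 conditional items (Appendix 5) and 24 women per arm (Section 5.0). The share active, the answers to items 18–21 and the VSQ standard deviation are not given and are assumed below.

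**1. Range of a raw sum.** Not active: 16 × 1 = 16. Active: 16 + 4 = 20. The conditional items are 4/20 = 20% of the larger maximum.

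**2. What creates the gap.** The form asks whether each matter bothered the woman in the past week. Take two women with identical answers to items 1–16. If the active one answers No to items 18–21, their raw totals are equal. A gap arises only from Yes answers. Activity is therefore necessary for the extra points but not sufficient, and the points themselves are reported symptom burden.

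**3. Raw-sum shift between arms.** Let d be the difference in share active and y the mean number of Yes answers on items 18–21 among active women. With items 1–16 equal in both arms, shift = d × y.
- d = 0.10: y = 0 gives 0, y = 1 gives 0.1, y = 4 gives 0.4.
- d = 3/24 = 0.125: y = 0 to 4 gives 0 to 0.5.
- d = 0.30: y = 2 gives 0.6, y = 4 gives 1.2.

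This applies to follow-up scores, and to changes if the arms' baseline shares are equal. The upper figures need every active woman to answer Yes to all four items, bleeding included.

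**4. Prorated score (percentage of answered items).** With x Yes on items 1–16, the gap for an active woman is (x + y)/20 − x/16 = y/20 − x/80. At x = 8 an inactive woman scores 8/16 = 50%.

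| y | Active woman's score | Gap (percentage points) |
|---|---|---|
| 0 | 40% | −10 |
| 1 | 45% | −5 |
| 2 | 50% | 0 |
| 3 | 55% | +5 |
| 4 | 60% | +10 |

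The gap is zero whenever y = x/4, that is, when both item sets are endorsed at the same rate. Per 10-point difference in share active, the shift is −1.0 to +1.0 percentage points.

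**5. Scale.** The standard error of a difference in means with 24 per arm is SD × √(2/24). SD 4 gives 1.155 and SD 6 gives 1.732. The largest raw shift per 10 points is then 0.4/1.155 = 0.35 of a standard error, or 0.4/1.732 = 0.23. The extreme case (30 points, all four Yes) gives 1.2/1.155 = 1.04 or 1.2/1.732 = 0.69. These are shifts in means; a rank test, which Section 12.0 also allows, was not worked through.

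**6. What the alternatives would cost.** Comparing only items 1–16 puts every woman on the same items. It also removes 4 of 20 items, including pain during sexual activity (item 19), from a measure chosen partly for sexual impact, and the documents do not describe that shorter score as validated. Adding a not-applicable box to the Appendix 1 scale alters an instrument that Section 3.0 calls validated. It also replaces an ambiguous 0 with a subgroup defined after randomisation. Section 3.0 schedules the patient questionnaires together, so item 17 can already be read beside a 0 on that scale. It is an imperfect guide, because it asks about activity with a partner and not about intercourse as such.

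**The case for a change.** The strongest case for a change is that the trial is open to patients, the rule is unstated, and a scoring choice made after the data are seen is open to challenge. Activity at follow-up is a plausible consequence of treatment. Section 2.0 describes lichen sclerosus as a cause of introital narrowing and dyspareunia. Table 3 cites a laser study in vaginal atrophy in which 85% of a group not sexually active beforehand reached a normal sexual life. One sentence in Section 12.0 would settle the matter.

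Part of this stands: the documents give no rule, and activity can change after randomisation. The rest is weaker.
- The Table 3 study is listed only as prospective and concerns another indication, so it shows no between-arm difference. The risk list in Section 8.0 names potential harms and allows sexual response to change in either direction.
- The raw sum is assumed. The plan cites a validation source for the instrument, which may carry the rule, so no faulty rule has been shown.
- Pain severe enough to make a woman stop having sex has another route into the results. Section 1.0 counts new or worsening dyspareunia as a complication, not confined to one arm, at 6 weeks, 6 months and 1 year.
- Neither the 16-item score nor the extra response box is a clear improvement; each trades one difficulty for another.

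**Conclusion.** This is a gap that analysts fill sensibly, and no change to the plan follows. The missing rule concerns one of several secondary outcomes, and the Skindex-29 sample size does not depend on it.

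Under an assumed raw sum, the shift is 0 to 0.4 points per 10-percentage-point difference in share active, at most 0.35 of a standard error if the SD is 4 to 6. It nears one standard error only if a 30-point difference in activity is combined with a Yes from every active woman on all four items. Under proration the shift can take either sign, and it vanishes when the two item sets are endorsed equally. None of these inputs is in the documents, and the direction cannot be foretold.

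Item 17 is recorded at each VSQ visit, so activity can be tabulated by arm and any dependence of the total on it seen. The same record helps in reading zero scores for pain with intercourse. The conclusion would differ if the plan had adopted a scoring rule shown to mislead, but it states none.
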